### **Cardiovascular Fitness Assessment**

The YMCA test uses an “extrapolation” method in which heart rate workload values are obtained at two to four points and extrapolated to predict workload at estimated maximum heart rate (220 - age). VO2 max is then calculated from predicted maximum workload. For YMCA submax,  $R=0.86$ ,  $SEE=10\%$  of the predicted when compared to VO2 max protocols. In addition to this calculation, inspired and expired gases will be sampled during the YMCA test by a COSMED metabolic CPET via a facemask. Oxygen and carbon dioxide excretion will be measured allowing for %VO2 throughout the test as well as a measurement anaerobic threshold.

### **Behavioral and Self-Report Data**

The analysis plan for behavioral performance will include the following dependent variables: semantic fluency performance and the motor tests, MOCA, and VO2 submax, and each self-report outcome. Paired t-tests will be performed to test for a pre- to post effect on fluency and motor skills. Similarly, subscale scores and total scores will be evaluated pre to post intervention for each self-report measure. Spearman’s correlations ( $r_s$ ) will be used to correlate behavioral performance to primary outcomes and a mixed regression will be used to assess the influence of session (pre and post) on outcomes.

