*Control Group:* A random subset of participants will be in a 12-week wait-list control. These participants will undergo the same scanning procedures as described above without cognitive or physical function testing. After 12-weeks these participants will come in and undergo the pre-assessment, 12-week exercise intervention and post assessment as described above.

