### **Inclusion/Exclusion Criteria**

Prior to beginning any portion of this study, we must receive a physician, physician assistant, or nurse practitioner's written medical approval for participation in the fitness assessment and/or exercise intervention. We will provide a letter to sign explaining the study protocol. The key inclusion criteria and final participant pool will consist of right-handed English-speaking individuals ages 18 to 80. Older participants will be sedentary as defined by <40 min/week of aerobic exercise. Additionally, participants will be non-demented and will have no cognitive-executive function deficit (MoCA  $\geq$  26). Further, those with severe diabetes requiring insulin will also be excluded. However, those with less severe, controlled diabetes that meet our physical and cognitive function inclusion criteria will be allowed to participant. Participants must not have conditions incompatible with MRI (including but not limited to, ferrous metal implants, cardiac pacemakers or similar devices, claustrophobia, morbid obesity). Potential participants with major psychiatric disorder (including but not limited to psychosis, major depression, bipolar disorder) by history will be excluded.

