## **7. Statistical Analysis:**

### **Statistical Analysis for Specific Aim 1**

Specific Aim 1 is to determine whether there will be a statistically significant difference in the cerebral perfusion data between the two groups (Spin and Control) following the intervention. We will assess the perfusion values jointly using a linear mixed-effects model to determine whether the mean change in perfusion between the groups is significantly different. For the model the fixed effect will be group (Spin vs Control) and the random effect will be time (Pre vs Post). We expect that modeling the outcomes jointly will increase the statistical power. This model will enable us to estimate the

overall effects of time and the interventions, and most importantly, how the effects of the interventions differ with time. Additional analyses will use multiple regressions to describe the effect of participant demographics such as gender, race, age, hypertensive status as well as MoCA score. A false discovery rate (FDR) of  $q = 0.05$  will be calculated and used to correct for multiple tests and effect sizes will be computed.

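### MoCA is both an entry filter and a behavioural outcome judged by session alone, so a within-arm MoCA change cannot be attributed to exercise

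*Combined protocol and SAP*

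**What the plan says.** Under Inclusion/Exclusion Criteria (section 6), "participants will be non-demented and will have no cognitive-executive function deficit (MoCA" must be 26 or above). Under Behavioral and Self-Report Data (section 7), the dependent variables are "semantic fluency performance and the motor tests, MOCA, and VO 2 submax, and each self-report outcome".

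That section names two kinds of change analysis. The first is "Paired t-tests will be performed to test for a pre- to post effect on fluency and motor skills", with similar pre-to-post evaluation of the self-report scales. The second is that "a mixed regression will be used to assess the influence of session (pre and post) on outcomes". Neither sentence has a group term or a group-by-session term.

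The cognitive tests described in section 5, from Verbal Fluency to Crystallized Word Knowledge, do not include MoCA. No section says when a pre or a post MoCA is taken. MoCA also appears as a descriptor in the additional regressions for Aim 1 ("hypertensive status as well as MoCA score") and for Aim 2. For the wait-list group, the Interventions text says: "These participants will undergo the same scanning procedures as described above without cognitive or physical function testing".

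**The concern.** When people are admitted because a score was high enough, some were admitted partly because of favourable measurement error on that occasion. If the same score is then used as the starting point, the next measurement falls on average with no true change. A model that tests session alone attributes that fall to the period of the intervention. Practice with the test pushes the other way, and the plan measures neither effect.

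A second, separate issue is room to improve. If the scale ends at 30, everyone starts within 4 points of the top.

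At stake is the reading of one secondary cognitive outcome. A within-arm fall could be taken as harm from an intervention meant to help, a real gain could be hidden, or a practice gain could be credited to exercise.

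**Working it through.** No figure in the plan rests on MoCA, so there is none to reproduce. The check asks how large the artefact could be, and when it disappears.

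**Inputs from the documents.** Cut-off 26 (Inclusion/Exclusion Criteria). 44 participants per group in the behavioural power text (Power Analysis and Sample Size), used only to scale the illustration.

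**Assumed inputs, not in the documents.** Mean of the screened people 25-27, SD 2.5-3, test-retest reliability 0.75-0.92, scale maximum 30, no true change and no practice effect. A wider grid is given below.

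**Formula.** Take a true score plus independent error at each occasion, screened mean μ, SD σ, reliability ρ, and selection on a rounded score of at least 26 (a raw score of at least 25.5). Then

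expected change = −(1 − ρ) × σ × λ(z), with z = (25.5 − μ)/σ and λ(z) = φ(z)/(1 − Φ(z)).

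Central case, μ = 26, σ = 2.5, ρ = 0.75:
- z = −0.5/2.5 = −0.20
- λ = 0.391/0.579 = 0.675
- expected change = −0.25 × 2.5 × 0.675 = −0.42

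Simulation with scores rounded to whole points and capped at 30 gives −0.45; rounding accounts for the small difference.

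**Results when the screening score is the pre value (simulation).**

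| Setting | Spurious mean change |
|---|---|
| Mean 25-27, SD 2.5-3, reliability 0.75-0.92 | −0.11 to −0.70 |
| Mean 24, SD 2-3, reliability 0.6-0.9 | −0.29 to −1.39 |
| Mean 26, same SD and reliability | −0.15 to −0.84 |
| Mean 28, same SD and reliability | −0.05 to −0.43 |

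For scale only: in the central case a two-sided paired test at 0.05 with 44 people and no true change is significant in 42% of trials. Over the first row of the table, such a test declares a decline in about 11-67% of trials. The plan does not name a paired test for MoCA. With two occasions, complete pairs and a participant random intercept, a session-only mixed model tests the same contrast, so the figures are a fair proxy if the mixed regression is applied to MoCA.

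**What removes or offsets it.**
- A fresh baseline MoCA, taken after eligibility is settled, gives an expected spurious change of 0.00 (at most 0.007 in absolute value in any setting).
- A practice gain of 0.5 points brings the central case to 0.00. A gain of 1.0 reverses it to +0.42.
- With two randomised arms of 44, both tested twice, the between-arm difference is 0.00 on average and its false-positive rate is 4.9% at a nominal 5%.

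**Ceiling.** Removing the cap changes the spurious decline by about 0.01 or less, and a cap with no entry filter gives about 0.00. The cap does compress gains: between arms in the central case, a true +1.0 shows as +0.86 and a true +2.0 as +1.60.

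**The case against.** The strongest reply is that the key premise is inferred. MoCA is missing from the listed battery, but by that logic the plan provides no post value either, so the list may simply be incomplete. A MoCA given at both the pre and the post evaluation would remove the regression to the mean. This stands: the decline is conditional on an unstated choice. Even its direction is open, because a modest practice gain cancels it and recruitment from research registries may put the screened mean well above the cut-off.

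It can also be said that the mixed-regression sentence might not cover MoCA, since the same sentence also refers to primary outcomes. If so, MoCA is a listed dependent variable with no change analysis, and the wording still needs settling.

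Randomised arms share the shift equally, so a comparison of arms would be unbiased. That is correct, but the section states no such comparison. It would also be unavailable against the wait-list group, which has no cognitive testing over its wait.

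A reader might infer four stronger claims that the documents do not support:
- That the plan will produce a decline. This needs the screening score as the pre value and little practice effect, and neither is stated.
- That the ceiling causes a decline. The calculation shows that it does not.
- That the paired-test error rates are properties of this trial, or could be scaled up to the 108 expected completers. Paired tests are named for fluency and motor skills, and 108 counts completers across all arms.
- That the MoCA regressions in Aims 1 and 2 are wrong. Restricting scores to 26 and above costs precision in a descriptive analysis; it is not an error.

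**Conclusion.** The point holds in conditional form and is minor. MoCA is both the selection variable and a listed outcome, and the section offers no between-arm contrast for its change. If the screening score is the pre value, regression to the mean can produce a spurious within-arm fall of about 0.1 to 0.7 points under the assumed ranges. It is smaller when the screened mean is higher, and is offset or reversed by a practice gain of 0.5 to 1 point. If a fresh baseline is taken, that fall vanishes, but practice and time remain mixed with exercise in any within-arm change. The ceiling is a separate limit on measurable benefit, assuming a 30-point maximum. All distributional inputs are outside assumptions. No aim, hypothesis or power figure uses MoCA.

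**What to change.** In Behavioral and Self-Report Data, choose one of two routes.

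1. Keep MoCA as an outcome. State that it is analysed only as the between-arm difference in pre-to-post change (the group-by-session term), among arms tested at both times. Name the comparator, because the wait-list group is not tested over its wait. State that the pre value is a MoCA taken after eligibility is confirmed, not the eligibility score. Cost: a few lines of text and one short repeat test per participant.

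2. Remove MoCA from the dependent variables and keep it for screening and description. Cost: one line of text and the loss of one weak secondary outcome. Semantic fluency, which is not an entry criterion and already has a power calculation, continues to carry the cognitive question.

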### **Crystallized Word Knowledge**

1. *American National Adult Reading Test (ANART)*: reading test used to help assess intelligence.

All cognitive testing will take place in the primary laboratory of the PI at the Atlanta VA Medical Center. All evaluations will be done by the PI or appropriate study staff. Additionally, to evaluate efficacy of interventions participants will self-report on:

1. Mac-Q- 6 item questionnaire to asking participants to describe their ability to perform memory task as compared to when they were in high school.
2. Behavior Rating Inventory of Executive Function (BRIEF)- Assesses self reported impairment of executive function task related to activities of daily living.
3. Self-Efficacy for exercise scale - a 13-item instrument that measures self-efficacy barriers to exercise,
4. Epworth Sleepiness Scale- self report used to determine the level of daytime sleepiness.
5. Apathy Index (MAI)- 14 item self-report instrument that measures overall apathy and participants interest in new things.
6. Pittsburgh Sleep Quality Index- 10 item questionnaire examining participants sleep habits over the past month.
7. Patient Health Questionnaire (PHQ-9) – 9-item instrument that screens for signs and symptoms of depression.
8. Pelvic Floor Distress Inventory Questionnaire (PFDI-20) – 20 item questionnaire that screens for bowel, bladder, or pelvic symptoms.

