above processing and modeling at the ROI level as it renders more detection power and is computationally less intensive. From a statistical standpoint, we will compute the F score to test the significance of overall fitting of the model, and we will also obtain the  $t$  score for each predictor (perfusion and CVR) to test the significance of their association with change in measured variable ( $\Delta$ BOLD). To evaluate responsiveness to training and its impact on the model, post hoc analysis will include stepwise multiple regression to evaluate delta VO2 on perfusion and CVR in a-priori ROIs as well as behavioral outcomes.

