### **Power Analysis and Sample Size**

For Aim 1, we used preliminary data comparing older active adults to older sedentary adults. Effect size for difference in inferior frontal perfusion for a small sample ( $n=10$ ) was  $d=2.740$ . If this effect size is taken as an estimate of the effect size for change in the Spin group with  $n=44$  and  $\alpha$  FDR-corrected to 0.0261, then power approaches 1.00. A more conservative estimated change in perfusion being half the effect, with the standard deviation remaining constant, would produce an effect size of 1.370. With the same  $n$  and  $\alpha$  as above, the power still approaches 1.00. The required effect size to achieve a power of 0.80 would be  $d=0.5$ , which would seem quite achievable given our preliminary data. Hence, the power should be more than adequate and seems plausible based on what we know. Because we want to maintain sensitivity at this level, the study is powered mainly to this Aim, while power for Aims 2 and 3 is more than adequate. For

example, for Aim 3, with  $\alpha < .05$ , minimum power of 0.80 and 88 subjects, we have the power to detect an increase in  $R^2$  as small as 0.111 in each ROI. We have detected significant correlations between BOLD response in M1 and IFG with smaller sample sizes (n=36 and n=41, respectively). Accounting for much less than 11% of the variance in criterion variables with the predictors would be too little variance to provide information useful for the design of future clinical trials. Hence, we should have the power to detect effects large enough to impact future clinical trials.

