For behavioral data, we estimate the effect size for semantic fluency from 2 sources of data using the same treatment we will use for this study. For our lab the effect size for change in the Spin group was  $d=1.804$ , and for the preliminary data from an ongoing study the effect size for change in semantic fluency was  $d=1.410$ . Using the more conservative of the two estimates,  $n=44$  and a FDR corrected  $\alpha=0.0261$ , power approaches 1.00. Again, an effect size of  $d=0.5$  would achieve a power of 0.80, which seems quite achievable given the large effect sizes in two independent samples. Use of the Control in this instance is problematic because of a large negative outlier, yielding a large negative mean (-2.000, indicating a loss of semantic fluency) and a large standard deviation. Even so, these data yield an effect size of  $d=0.886$ , but these data are not stable enough to yield a good estimate of between-group effect size. With  $n=44$  per group and  $\alpha=.05$  (FDR corrected), an effect size of  $d=0.64$  would yield a power of 0.80. Based on the strong effect size for Spin, we believe this is an achievable effect size for a between-group analysis based on what we know about the Spin intervention.

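### The behavioural and self-report analysis states only pre-to-post tests and no between-group test, although the power section anticipates a between-group analysis of semantic fluency

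*Combined protocol and SAP*

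**What the plan says.** The only dedicated analysis text for these outcomes is Behavioral and Self-Report Data in section 7. It lists semantic fluency, the motor tests, MoCA, submaximal VO2 and every self-report outcome as dependent variables. Its methods are:

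- for fluency and motor skills, "Paired t-tests will be performed to test for a pre- to post effect on fluency and motor skills";
- for each questionnaire, total and subscale scores compared before and after the intervention;
- Spearman correlations with the primary outcomes;
- "a mixed regression will be used to assess the influence of session (pre and post) on outcomes", with no further terms given.

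The Aim 3 text adds that "post hoc analysis will include stepwise multiple regression", relating change in VO2 to perfusion, CVR and behaviour. That is not a comparison of arms.

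Three other places bear on the point.

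- Power Analysis and Sample Size first powers the fluency change within Spin (n=44, alpha 0.0261). It then gives d=0.64, 44 per group and power 0.80, and says "we believe this is an achievable effect size for a between-group analysis".
- The self-report list under Crystallized Word Knowledge is introduced with "to evaluate efficacy of interventions participants will self-report on".
- The Aim 1 analysis does name the arms: "For the model the fixed effect will be group (Spin vs Control"). Aim 2 does the same for CVR.

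**The concern.** A change from before to after in one arm is the sum of any exercise effect and everything else that moves scores over 12 weeks: familiarity with the tests, time, and being in a study. Only a concurrent comparator removes the part common to both arms. If the behavioural section is followed as written, a significant paired test could be reported as a benefit of aerobic exercise when it shows only that scores moved.

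The documents give no ground for taking change without aerobic exercise to be zero. The one comparator fluency change they report (mean -2.000) is driven by an outlier, and the plan itself says "these data are not stable enough to yield a good estimate of between-group effect size".

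The gap matters most where the plan points to a treatment claim, namely semantic fluency and the self-report measures.

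**Working it through.** **Text check.** Section by section, the between-group content is as follows.

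| Outcome | Arm comparison written? | Sign that one is intended? |
|---|---|---|
| Perfusion (Aim 1), CVR (Aim 2) | Yes, Spin vs Control | Yes |
| Semantic fluency | No | Yes, in the power section |
| Self-report | No | Efficacy purpose stated |
| Motor tests | No | None found |
| MoCA, submaximal VO2 | No; not named for the paired t-tests either | None in the analysis text |

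**Inputs.** From the power section: 44 per group; alpha 0.0261 for the within-Spin fluency calculation; alpha written as .05 with an FDR label for the between-group one; d=0.5 (within) and d=0.64 (between), each for 80% power. From Participant selection: 108 completers and three conditions. Sidedness is not stated, so two-sided tests are assumed. Effect sizes are in SD of change.

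**The plan's own figures.**

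- Within Spin, noncentrality is d√44 on 43 df. At alpha 0.0261, d=0.5 gives power 0.84, and 80% is reached at d=0.476, which rounds to the stated 0.5.
- Between groups, noncentrality is d√(44/2) = 0.64 × 4.690 = 3.00 on 86 df. Power is 0.77 at alpha 0.0261 (0.78 by normal approximation) and 0.84 at 0.05. The stated 0.80 lies between, at alpha of about 0.034. Both levels are therefore carried below.

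**What a shared shift does to the paired test.** Suppose exercise has no effect and scores shift by s. The documents give no usable value of s, so 0.1 to 0.5 is an assumed range. Noncentrality is s√44 = 6.633s on 43 df; the critical t is 2.304 (alpha 0.0261) or 2.017 (alpha 0.05).

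| s | 0.1 | 0.2 | 0.3 | 0.4 | 0.5 |
|---|---|---|---|---|---|
| s√44 | 0.66 | 1.33 | 1.99 | 2.65 | 3.32 |
| P(significant), alpha 0.0261 | 6% | 17% | 39% | 64% | 84% |
| P(significant), alpha 0.05 | 10% | 25% | 49% | 74% | 90% |

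For a between-group test of change, the expected difference is s - s = 0 for any s, so it keeps its nominal level.

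**What the between-group test costs.** Effect size needed for 80% power:

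| Test | alpha 0.05 | alpha 0.0261 |
|---|---|---|
| Paired, n=44 | 0.43 | 0.48 |
| Difference in change, 44 per group | 0.60 | 0.66 |
| Difference in change, 36 per group | 0.67 | 0.74 |
| ANCOVA on baseline, 44 per group, r=0.8 | 0.57 | 0.63 |
| ANCOVA on baseline, 44 per group, r=0.5 | 0.52 | 0.58 |

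The 36 is 108/3, assuming equal allocation. The ANCOVA rows use the variance ratio 2(1-r)/(1-r²) = 2/(1+r), so d is multiplied by √(2/(1+r)): 1.155 at r=0.5 and 1.054 at r=0.8, on 85 df. The pre/post correlation r is an assumption.

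**The case against.** **The plan is incomplete rather than wrong.** For fluency, the power section shows that a group comparison is foreseen, and the mixed regression may contain a group term that was not written down. This is fair for fluency. A reader might infer that the investigators intend no behavioural arm comparison at all; the documents do not support that. But the only factor named is session, and the section meant to specify the test does not do so. For self-report and motor outcomes no arm comparison is mentioned anywhere.

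**Practice effects are already limited.** Verbal Fluency lists alternative letters and categories, the walking-while-talking task varies its starting letter, and the in-scanner fluency stimuli differ before and after with matched difficulty. These steps may reduce item-specific practice. They do not show it to be zero, and they leave general familiarity and time effects in place.

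**The paired tests might pool the arms.** The behavioural section does not say. A reader might infer false-positive rates for 88 pooled participants, which would be higher than those shown. The support is weak: the plan's own pre-to-post fluency calculation is for Spin with n=44, and the 88 belongs to the Aim 3 regression.

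**The outcomes are secondary.** This stands. The three aims are imaging aims, and of Aim 1 the plan says "the study is powered mainly to this Aim".

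**Conclusion.** The concern holds as a gap in specification that would lead to a weaker analysis if the text were followed. No between-group test is written for any behavioural or self-report outcome, and the stated pre-to-post tests cannot attribute a change to aerobic exercise.

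The rates of 6 to 84% (alpha 0.0261) or 10 to 90% (alpha 0.05) only illustrate the exposure. They rest on an assumed shared shift of 0.1 to 0.5 SD, two-sided testing and 44 Spin participants. The gap itself does not depend on them, and they are not evidence that a practice effect of that size exists here.

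A reader might also infer that the trial's main conclusions are at risk from this. They are not: the perfusion and CVR analyses name group, and no imaging aim depends on these tests. The change should be made, but it does not bear on the primary question.

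**What to change.** In Behavioral and Self-Report Data, make the test for each behavioural and self-report outcome the Spin-versus-comparator difference in change. Either ANCOVA of the post score on group and baseline, or a group-by-session term with a participant random intercept, would serve. Keep the paired within-arm changes as description.

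Name the comparator, which needs concurrent pre and post behavioural data. The stretching arm (Specific Aims; also the content described under Interval Exercise Group) fits, since nothing exempts it from pre and post testing. The wait-list group in the Control Group paragraph does not, because it has no cognitive or physical-function assessment while waiting. Specific Aims describes two conditions and Participant selection three, so these passages and Interventions must be reconciled first.

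If the comparator is tested concurrently, the change is to text only. If it is the wait-list group, the waiting-period data would not exist and rewording alone would not be enough.

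The price is power. With 44 per group, 80% power needs d of 0.60 (alpha 0.05) or 0.66 (alpha 0.0261) instead of 0.43 or 0.48; with 36 per group it needs 0.67 or 0.74. The plan already accepts 0.64, which covers only the first of these four between-group figures. ANCOVA recovers part of the loss.

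The new test removes shifts common to both arms but not expectation that differs by arm. With 44 per group, an assumed arm difference of 0.1/0.2/0.3 SD with no exercise effect would still be significant 4/10/20% of the time at alpha 0.0261, or 8/15/28% at 0.05. The report should say so.

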#### **4. Specific Aims:**

The study will enroll 134 older, sedentary adults. Participants will be pseudorandomized to one of two 12-week intervention conditions: Aerobic Exercise or Stretching.

**Specific Aim 1:** To determine the effect of a 12-week aerobic exercise intervention on changes in cerebral perfusion using arterial spin labeling in older Veterans.

*Hypothesis:* Compared to a non-aerobic intervention Control group, the aerobically trained group will have increased basal perfusion in areas that demonstrate age-related decline and are malleable to aerobic exercise (inferior frontal and motor cortices).

**Specific Aim 2:** To determine the effect of a 12-week aerobic exercise intervention on changes in cerebrovascular reactivity using a hypercapnic CO2 response test in older Veterans.

*Hypothesis:* Following the interventions, aerobically-trained older adults will have increased CVR to CO2 in the inferior frontal and motor cortices when compared to controls.

**Specific Aim 3:** To quantify the impact of cerebrovascular perfusion and cerebrovascular reactivity on the BOLD response during task-based (cognitive executive and motor) fMRI.

*Hypothesis:* Perfusion and CVR will account for a significant portion of variability in the BOLD response during task-based fMRI both before and after the intervention.

*Measures for Specific Aim 3.*

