## **6. Participant selection:**

The study will enroll sedentary older adults and young adults as a comparison group for the MRI scans. Older adult participants will be pseudo-randomized to one of three 12week intervention conditions: Aerobic Exercise, Interval Exercise, or Control. The pre and post evaluations will be conducted over 2 days during a 1-week period. Each day will last no more than 2 hours. The investigators expect a dropout rate of anywhere from 15-20% of participants. To ensure completion of study by 108 participants, as many as 134 subjects may be enrolled.

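### The behaviour-to-imaging Spearman correlations state no arm, session or score type, so pooling change or post values over arms could pass off the treatment effect as an association between people

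*Combined protocol and SAP*

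**What the plan says.** Section 7, Behavioral and Self-Report Data, lists semantic fluency, the motor tests, MoCA, submaximal VO2 and the self-report scales as dependent variables. It plans paired t-tests from pre to post. It then says that Spearman correlations "will be used to correlate behavioral performance to primary outcomes and a mixed regression will be used". The stated purpose of that regression is "to assess the influence of session (pre and post) on outcomes". That is the whole specification of the correlations. The mixed regression in the same sentence concerns session; it has no stated arm term and does not adjust the correlations.

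Nothing elsewhere fills the gap. The Aim 1 and Aim 2 models have a group term, but only for perfusion and CVR. The post hoc stepwise regression under Aim 3 concerns change in VO2.

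The comparator is described in more than one way. Section 4 has "one of two 12-week intervention conditions: Aerobic Exercise or Stretching". Section 6 has "one of three 12week intervention conditions: Aerobic Exercise, Interval Exercise, or Control". Under Interventions, the Interval Exercise paragraph describes stretching, toning and balance work, while the Control Group is a wait-list scanned "without cognitive or physical function testing" over its 12 weeks. Yet Power Analysis and Sample Size cites preliminary fluency data in Control and plans a between-group fluency comparison: "With $n=44$ per group", an effect of 0.64 is said to give power 0.80. It judges this achievable "Based on the strong effect size for Spin".

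**The concern.** The plan expects Spin to raise perfusion and fluency alike. If two measures both shift in one arm, a correlation over both arms picks up arm membership. Spin participants tend to be high on both measures and comparators low on both, even when, inside each arm, a person's perfusion change says nothing about that person's fluency change.

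Session raises a second problem. A plain rank correlation cannot take the pre and post rows of one person without counting that person twice.

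The Background argues that exercise benefits are partly mediated by perfusion and CVR. A significant behaviour-to-perfusion coefficient would probably be read as support for that, when it might show only that Spin moved each measure separately. Because the text leaves arm, session and score open, the choice could also be made after the data are seen.

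**Working it through.** **Inputs.** From Power Analysis and Sample Size: 44 per group; 0.64, the between-group behavioural effect; 1.410, fluency change in Spin; 0.886, a preliminary fluency effect using Control data that the plan itself calls unstable; 1.370, perfusion. The last is half of 2.740, a cross-sectional active-versus-sedentary difference from a small sample (n=10) that the plan takes as a change in Spin. Assumed here: 0.64 for perfusion as well; the 1.0/1.0 scenario; no change in Control when 1.37 and 1.41 are used as between-arm shifts; two-sided tests; normal data; test-retest correlations of 0.5 to 0.8.

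**Step 1: the plan's nearest figure.** The documents give no figure for the correlations, so I checked the between-group power. By the normal approximation, 0.64 × √(44/2) = 3.002. The two-sided critical value at the plan's FDR-corrected alpha of 0.0261 is 2.225, and Φ(3.002 − 2.225) = 0.781. The exact t calculation gives 0.768 at 0.0261 and 0.843 at 0.05. The stated 0.80 is met to within about two points by the first.

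**Step 2: expected coefficient, pooled over arms.** For two equal arms, zero correlation within each, and between-arm shifts d1 and d2 in within-arm SDs:

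r = (d1·d2/4) / √[(1 + d1²/4)(1 + d2²/4)]

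- 0.64/0.64: 0.1024/1.1024 = 0.093
- 1.0/1.0: 0.25/1.25 = 0.20
- 1.37/1.41: 0.4829/√(1.4692 × 1.4970) = 0.326

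**Step 3: how often Spearman is significant.** Simulation of 20,000 trials, change scores, 44 per arm, no association within either arm:

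| Shift, perfusion / behaviour | Mean pooled r_s | p<0.05, pooled | p<0.05, adjusted for arm |
|---|---|---|---|
| 0 / 0 | 0.00 | 5% | 5% |
| 0.3 / 0.3 | 0.02 | 5.5% | 5% |
| 0.5 / 0.5 | 0.06 | 8% | 5% |
| 0.64 / 0.64 | 0.09 | 14% | 5% |
| 1.0 / 1.0 | 0.20 | 48% | 5% |
| 1.37 / 0.886 | 0.24 | 61% | 5% |
| 1.37 / 1.41 | 0.34 | 92% | 5% |
| 1.37 / 0 | 0.00 | 5% | 5% |

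The last row shows that both measures must move. Testing at 0.0261 does not cure it: the pooled shares are then 9%, 38% and 87% at 0.64/0.64, 1.0/1.0 and 1.37/1.41.

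**Step 4: levels instead of changes.** Baseline values pooled over arms give 5% at any treatment effect. For post values, a shift of d in change SDs is d·√[2(1−ρ)] in level SDs, where ρ is the test-retest correlation. At ρ = 0.8 the factor is 0.632, so 1.37/1.41 becomes 0.87/0.89. Pooled post values at 1.37/1.41 are then significant in 92% (ρ = 0.5) down to 33% (ρ = 0.8).

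**Step 5: both sessions as independent rows.** With 2 × 44 × 2 = 176 rows and no treatment effect, the variance of the coefficient is inflated by about 1 + ρ². At ρ = 0.5, 1.96/√1.25 = 1.753, a rejection rate of about 8%. At ρ = 0.8, 1.96/√1.64 = 1.530, about 13%. Simulation gives 8% and 12%. With effects of 1.37/1.41 the rate is 93% to 40% over the same range of ρ. Pooling pre and post rows within Spin alone gives 93% to 37%, so naming the arm without the session is not enough.

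**Step 6: precision after the fix.** By Fisher z, 80% power at two-sided 0.05 needs tanh(2.80/√84) = 0.30 adjusted for arm (n = 88), or tanh(2.80/√41) = 0.41 within one arm of 44.

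**The case against.** The strongest reply is that the plan never says the arms are pooled. Baseline correlations, or change-on-change within Spin, fit the text equally well and carry no artefact. That stands: pooling is one permitted reading, not a commitment.

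The largest figure also rests on borrowed inputs. The 1.41 is a change within Spin, and the 1.37 is half a cross-sectional contrast used as such a change; neither is a between-arm effect. This stands too. At 0.64, the between-group effect the plan calls achievable for behaviour, the inflation is to 14%.

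If Control is the wait-list group, there is no cognitive change over the control period to pool with Spin, and the calculation does not apply. Against this, the power section uses Control fluency data and plans a between-group fluency comparison, so the statistical text expects cognitive data in the comparator. The documents do not settle it.

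A reader might infer that the pooled coefficient will show a link whenever exercise moves both measures. The figures do not support that: at 0.64/0.64 about 86% of trials show nothing significant, and at 0.3/0.3 the rate is close to nominal. A reader might also infer that the study's main mechanistic conclusion is at risk. It is not: Aims 1 and 2 use mixed models, Aim 3 uses its own regression of task BOLD on perfusion and CVR, and none depends on these coefficients.

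**Conclusion.** The gap is real, and it is more than missing detail, because a plain Spearman coefficient run on both arms' change or post values mixes the treatment effect into the association. Under that reading, with no association within either arm, about 14% of trials are significant at 0.64/0.64, 48% at 1.0/1.0 and about 92% at 1.37/1.41, against about 5% after adjustment for arm.

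These figures assume 44 per arm, a comparator with cognitive data, an effect of exercise on both measures and, for the last, no change in Control. Entering both sessions as independent rows is a separate error, with 8% to 12% rejection even without a treatment effect. The point affects the interpretation of a supporting analysis and should be settled before the data are seen.

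**What to change.** In Behavioral and Self-Report Data, state that:

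- each participant's pre-to-post behavioural change is correlated with their pre-to-post change in the imaging outcome, one record per person;
- the coefficient is a partial Spearman adjusted for arm (rank both changes, remove the arm means from the ranks, correlate the residuals);
- the within-arm coefficients are shown beside it as description;
- any level-to-level correlation uses pre-session values only.

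Reconcile Specific Aims, Interventions, Participant selection and the power section on which group is Control and whether it has cognitive data at both time points. Without that, the adjustment for arm cannot be defined.

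The cost is a sentence or two and no new data. Where both measures move, coefficients will be smaller than pooled ones. Precision is modest, as Step 6 shows, and the within-arm values more so. Even the adjusted coefficient is an association and should not be reported as evidence of mediation.
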